TIME	Within 4 weeks prior to enrollment	Within 6 weeks prior to treatment	Within 4 weeks prior to treatment	Within 4 weeks prior to treatment	Within 4 weeks prior to treatment	Day 0	Every 2 weeks	3-5 weeks after Initial Treatment	Every 2 weeks	1 month after the last treatment	3 months after the last treatment	6, 9, 12, 15, 18, 21, 24 months after the last treatment	
Informed consent	X												
Demographics	X												
Medical history	X				X(*4)			X		X	X	X	X
Physical exam	X				X(*4)			X		X	X	X	X
Performance status	X				X(*4)			X		X	X	X	X
Concomitant medications	X				X(*4)			X		X	X	X	X
Dose calculation					X								
Order SIR-Spheres microspheres					X								
CBC, differential, platelets	X				X(*4)	X	X	X	X	X	X	X	X
PT, PTT, and INR	X				X			X					
Serum biochemistry (*1)	X				X(*4)	X	X	X	X	X	X	X	X
LDH	X				X(*4)	X	X	X	X	X	X	X	X
Pregnancy test (*2)	X				X(*4)								
Study blood drawing						X(*3)				X(*3)	X(*3)		
Liver tumor biopsy			X										
CT scan of chest, abdomen and pelvis	X				X(*4)					X	X	X	X
MRI of abdomen	X				X(*4)						X	X	X
PET scan					X						X	X	X
Volumetric measurement					X								
Hepatic angiogram				X		X		X					
Tc-99 MAA study				X									
Treatment with SIR-Spheres microspheres						X		X					
Toxicities & adverse events					X(*4)	X	X	X	X	X	X	X	X

*1: Comprehensive metabolic panel including total bilirubin, SGOT (AST), SGPT (ALT), alkaline phosphatase, albumin, creatinine, BUN, glucose, calcium

*2: For females of childbearing potential.

*3: 100 ml blood for peripheral blood mononuclear cells, and 10 ml of blood for serum collection.

*4: Tests can be skipped if screening evaluation is performed within 4 weeks prior to scheduled treatment.

*5: If necessary.

*6: Exit visit can be skipped if follow-up visit is performed within 4 weeks.

1.0Background

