2.2 Study Endpoints

- (1) Response Rate: 60% stabilization rate (CR+ PR+SD) warrants future study.

(2) Adverse Events: Treatment-emergent and related serious adverse events, and Grade 3 and 4 laboratory abnormalities for safety assessments.

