3.0 Study Design

This is an open-label, uncontrolled single institution phase II study for metastatic uveal melanoma. Uveal melanoma patients who received one or less prior trans-arterial embolization treatment of hepatic metastasis are eligible. Patients will be stratified into two groups: Group A, no prior intra-hepatic arterial treatment, n=24; Group B, one prior hepatic trans-arterial embolization treatment, n=24. They will be treated with intra-hepatic arterial infusion of Yttrium-90 radioactive microspheres (SIR-Spheres® microspheres).

Within 4 weeks prior to radiosphere treatment, patients undergo the pre-assessment angiogram and technetium-99m-labelled macroaggregated albumin (^{99m}Tc -MAA) nuclear scan to block the collateral flow to non-target organs and to calculate the shunting rate to the lung. Once patients meet the eligibility criteria of the study, the radiosphere treatment will be given. The Yttrium-90 radioactive microsphere treatment generally consists of two sequential uni-lobar treatments, approximately 4 weeks (3 to 5 weeks) apart. In selected patients, if clinically feasible, a biopsy of hepatic metastasis will be obtained prior to radiosphere treatment to investigate the correlation between efficacy of treatments and molecular characteristics of metastatic uveal melanoma.

The side effects of Yttrium-90 radioactive microspheres will be monitored every 2 weeks for one month following each treatment and then every month for three months after the last radiosphere treatment. The efficacy of radiosphere treatment will be evaluated every 3 months from the last treatment for 2 years until disease progression or death.

If patients experience grade 3 toxicity after the first treatment with Yttrium-90 radioactive microspheres, the second radiosphere treatment will be held until the resolution of toxicity to grade 1 or less or for a maximum of 6 weeks. The dose of the second radiosphere treatment will be decreased by 50% for liver-related grade 3 toxicity. A dose reduction will not be considered for

grade 3 GI toxicity unless the next treatment is repeated to the same hepatic lobe. The study treatment will be discontinued for grade 4 toxicity or if patients do not recover from the grade 3 toxicity to at least a grade 1 within 6 weeks.

The study will require two years of accrual with an additional two years of follow-up for survival analysis.

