5.4 Radioactive microsphere treatment

Within 4 weeks after the flow study, selective internal radiation therapy (SIRT) using yttrium-90 SIR-Spheres® microspheres (radiosphere treatment) will be performed. Due to multiple, bilobar metastases, both right and left hepatic lobes need to be treated in the majority of patients. The goal of therapy is to treat the tumor bearing liver in 2 sessions. Treatments are preferentially done in a lobar fashion. In the setting of complex anatomy, fractionated whole liver therapy is used as an alternative. In general, the delivery of radioactive microspheres will require two sequential unilobar treatments separated by a period of 4 ± 1 weeks. The lobe to be treated first will be determined by the treating physicians. The radiosphere dose for each hepatic lobe will be determined based on the tumor volume in individual lobes.

In patients whose hepatic artery does not allow two separate sequential unilobar treatments, whole liver treatment via the proper hepatic artery may be performed if no extrahepatic arteries are identified distal to the catheter site intended for radioactive microsphere delivery. The dose will be delivered in two fractionated doses separated by 4 ± 1 weeks (fractionated whole liver).

If a prior hepatectomy has been performed leaving a single lobe for treatment, or if metastatic disease is confined to a single lobe, the entire dose will be delivered in a single session to the affected lobe.

Treatment will be administered on an outpatient basis with overnight, 23-hour observation permitted at the investigator's discretion. Patients will receive the supportive care as described in Section 7.

Approximately 100ml of blood specimens will be obtained for Peripheral Blood Mononuclear Cell (PBMC) collection prior to radiosphere treatment. Additionally, 10 ml of blood specimens will be obtained for serum collection prior to, and 1 hour after radiosphere treatment.

Blood tests including CBC with differential, comprehensive metabolic panel including total

bilirubin, SGOT (AST), SGPT (ALT), LDH, alkaline phosphatase, albumin, creatinine, BUN, glucose, calcium, and LDH will be ordered every 2 weeks for one month, then every month for three months to monitor treatment-related toxicity.

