5.5 One-month post-procedure visit

In 4 weeks (\pm 1 week) after the last radiosphere treatment (usually after the second radiosphere treatment), patients will be evaluated for treatment-related acute toxicity. Patient will also have a 1-month follow-up CT scan of the chest, abdomen and pelvis (with and without contrast) to assess extrahepatic disease.

Approximately 100ml of blood specimens will be obtained for PBMC collection. Additionally, 10 ml of blood specimens will be obtained for serum collection.

5.6 3-month post-procedure visit

Three months (\pm 2 weeks) after the last radiosphere treatment (usually after the second radiosphere treatment), patients will be evaluated for response to treatment and late toxicity. CT scan of the chest, abdomen and pelvis (with and without contrast); MRI of the abdomen (with and without gadolinium) and PET scan will be obtained.

Approximately 100ml of blood specimens will be obtained for PBMC collection. Additionally, 10 ml of blood specimens will be obtained for serum collection.

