The development of acute peptic ulceration is suggested by the recognized symptoms of ulcer disease and diagnosed by endoscopy. If this were to occur, the patient should be treated using best standard practice, including pain relief, gastric acid blocking drugs and intravenous fluids.

Treatment is the same as for any cause of acute peptic ulceration.

Delayed Serious Events

Radiation Pneumonitis

Microsphere shunting to the lungs can cause edema and fibrosis that may not be reversible. Extrahepatic shunting may be identified through the injection of ^{99m}Tc -MAA into the hepatic artery (20, 21). High levels of implanted radiation and/or excessive shunting to the lung may lead to radiation pneumonitis. This may be suspected if patients develop a non-productive cough several days or weeks after the implantation of SIR-Spheres® microspheres and is diagnosed by chest X-ray. Patients should be treated with systemic corticosteroids and supportive care until symptoms have subsided.

Radiation Hepatitis

The use of radiosphere leads to irradiation of both tumor and normal liver parenchyma. As a result, patients with diseases which compromise the functioning of the liver parenchyma or with very small lesions scattered throughout the normal parenchyma may be at greater risk of liver function impairment. Excessive radiation to the normal liver parenchyma may result in radiation hepatitis. This can be difficult to diagnose, and may appear many weeks after the implantation of SIR-Spheres® microspheres. It is suspected if there is unexplained progressive deterioration in liver function. The diagnosis can be confirmed by histological examination of core liver biopsy. If the diagnosis is suspected or proven then patients should be treated with systemic corticosteroids and supportive care until the inflammation settles.

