11.1.3 Adverse Event Reporting Period

The adverse event reporting period for this trial begins when the patient receives the first radiosphere treatment and ends 3 months after the last radiosphere treatment. All adverse events that occur in trial subjects during the adverse event reporting period specified in the protocol will be reported, whether or not the event is considered treatment-related.

In addition, even after the completion of adverse event reporting period, if investigators consider that patients develop a serious adverse event that would be possibly related to the study treatment, such SAE will be reported.

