11.2 Evaluation of Adverse Events

The Common Terminology Criteria for Adverse Events (CTCAE version 4.0) (http://ctep.cancer.gov/protocoldevelopment/electronic_applications/docs/ctcaev4.pdf) will be used to grade the maximum intensity of the event.

The acute toxicity assessment will be performed 1 month after the last radiosphere treatment. The patient will be re-evaluated for late toxicity at 3-month follow-up visit. After completion of the 3-month visit, patients will be followed every three months for 2 years for survival. Follow-up over the telephone will be allowed for this purpose. During this follow-up period, if investigators consider that patients develop a serious adverse event that would be possibly related to the study treatment, such SAE will be reported.

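### The text orders monthly toxicity and laboratory checks to month 3, but the schedule table has no month-2 assessment, so staff who follow the table leave about 9 weeks without liver tests

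*Combined protocol and SAP*

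**What the plan says.** Section 3.0 (Study Design) has side effects "monitored every 2 weeks for one month following each treatment and then every month for three months after the last radiosphere treatment". Section 5.4 lists CBC with differential, a metabolic panel with the liver tests, and LDH, and says these "will be ordered every 2 weeks for one month, then every month for three months to monitor treatment-related toxicity".

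The schedule table in the protocol summary is laid out differently. It marks CBC, biochemistry, LDH and toxicities in the two-weekly post-treatment columns, at the 1-month visit, at the visit "3 months after the last treatment", and every three months from month 6. It has no month-2 column, and no footnote supplies one.

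The visit sections match the table. Section 5.5 covers the 1-month visit. Section 5.6 covers the 3-month visit, where "patients will be evaluated for response to treatment and late toxicity". Section 5.7 moves to three-monthly visits. Section 11.2 says "The acute toxicity assessment will be performed 1 month after the last radiosphere treatment" and places the late toxicity assessment at the 3-month visit. It leaves out month 2 without contradicting it.

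The safety endpoint in Section 2.2 includes "Grade 3 and 4 laboratory abnormalities for safety assessments". The adverse event reporting period in Section 11.1.3 "ends 3 months after the last radiosphere treatment".

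**The concern.** Two operative instructions disagree about whether patients are assessed at month 2, and the protocol states no order of precedence. Staff commonly book visits and laboratory orders from a schedule table. Section 5.1 itself points to this one for the pre-study tests. With no month-2 visit described anywhere in Section 5, only the monitoring sentences in Sections 3.0 and 5.4 would prompt the draw.

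What is at stake is the detection of late liver toxicity. Section 8.4 warns that radiation hepatitis is hard to diagnose and can surface weeks after implantation. On recognition it says: "It is suspected if there is unexplained progressive deterioration in liver function". It recommends corticosteroids once the condition is suspected or proven, so earlier recognition changes care. Adverse event reporting is continuous to month 3, but an abnormality without symptoms enters the record only if blood is drawn. Safety is a primary objective, and laboratory grade 3 and 4 counts would depend on which instruction was followed for each patient.

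**Working it through.** The plan states no figure for this interval, so there is none to reproduce.

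**Inputs**
- 1-month visit: 4 weeks ± 1 week after the last treatment (Section 5.5), so day 28, range 21 to 35.
- 3-month visit: three months ± 2 weeks (Section 5.6). Three months is 3 × 365.25/12 ≈ 91 days, range 77 to 105.
- Month-2 draw, under the text only: about day 60.
- The table's two-weekly column prints no end date. It is read as ending at the 1-month visit, because it stands before that visit and Sections 3.0 and 5.4 limit two-weekly checks to one month.

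**Draws after the last treatment, to month 3**
- Text: weeks 2 and 4, months 2 and 3 = 4.
- Table: weeks 2 and 4, month 3 = 3.

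**Length of the gap under the table**
- Nominal: 91 − 28 = 63 days, or 9 weeks.
- Shortest: 77 − 35 = 42 days.
- Longest: 105 − 21 = 84 days. If a day-28 draw is still taken after an early 1-month visit, this becomes 105 − 28 = 77 days.
- With a month-2 draw, the nominal gap splits into 60 − 28 = 32 days and 91 − 60 = 31 days.

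**Delay in seeing an abnormality that persists** (assumption: onset uniform over days 28 to 91)
- Table: mean 63/2 = 31.5 days, maximum 63.
- Text: mean (32² + 31²)/(2 × 63) = 1985/126 = 15.8 days, maximum 32.

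**Share of transient episodes seen** (same assumption; the episode lasts d days and is seen only if a draw falls within it)
- Table: min(d, 63)/63.
- Text: [min(d, 32) + min(d, 31)]/63.

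| Duration d | Table | Text |
|---|---|---|
| 14 days | 14/63 = 22% | 28/63 = 44% |
| 28 days | 28/63 = 44% | 56/63 = 89% |
| 42 days | 42/63 = 67% | 63/63 = 100% |
| 63 days or more | 100% | 100% |

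The documents give no episode durations, so the rows show a range and not an estimate. The shares apply only to episodes that begin in the gap.

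**The case against.** The strongest reply is that the protocol already orders the test. Section 5.4 specifies the post-treatment laboratory work in full without referring to the table, so this is an incomplete summary table and not a hole in the safety plan. That is right as far as it goes: the gap opens only if staff follow the table. But the table is an operative part of the protocol, the visit sections share its omission, and nothing says that the text prevails.

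The table's two-weekly column could also be read as open-ended and so cover month 2. That is possible, but its position and the one-month limit in the text make it the less natural reading.

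Section 5.4 could be read as running to month 4, which would change the count of 4 draws against 3. Section 3.0 and the 3-month reporting period favour month 3, and month 2 is required and missing from the table on either reading.

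The percentages depend on assumed onset and durations, and no incidence of new grade 3 or 4 values between months 1 and 3 is given. That stands: the number of events missed cannot be estimated and may be small. The institutional series in Section 1.8 reports raised hepatic enzymes in 5 of 12 patients, but at 1 month, so it does not supply the missing rate.

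Other safeguards narrow the consequence. Events already recorded are followed under Section 11.6, and no study dose remains to be decided after the last treatment. What is left exposed is a new abnormality without symptoms.

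**Conclusion.** The point holds. The text requires a month-2 toxicity and laboratory check that the table omits, and the protocol does not say which governs. Following the table leaves a nominal 63 days without routine liver tests (42 to 84 days across the windows) and roughly doubles the mean delay in seeing a persistent abnormality, from 15.8 to 31.5 days. Progressive hepatitis would be found later, not missed. Grade 3 or 4 values that start after month 1 and resolve before month 3 could go unrecorded. These figures rest on uniform onset, on the two-weekly column ending at the 1-month visit and on monthly checks ending at month 3. The conflict itself does not depend on the onset assumption. It should be corrected, but it has no bearing on efficacy, sample size or the two-stage stopping rule.

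**What to change.** Let the text schedule govern, and make three edits:

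1. Add a month-2 column to the schedule table, marked for CBC with differential and platelets, serum biochemistry, LDH, and toxicities and adverse events.
2. Name the month-2 check in Section 11.2.
3. Reword Section 5.4 so that the monthly tests run until three months after the last radiosphere treatment. This matches Sections 3.0 and 11.1.3 and removes the month-4 reading.

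The cost is wording in three places and at most one blood draw per patient, so at most 48 draws across the 48 planned patients, all of which the text already orders.

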4.0 Selection of Patients

4.1 Inclusion criteria

- 4.11 Histologically confirmed metastatic uveal melanoma in the liver. Patients must have at least one untreated, or progressed liver metastasis that is ≥ 10 mm in longest diameter by spiral CT scan or MRI. The total volume of the tumors must be less than 50% of the liver volume.
- 4.12 Either no previous trans-hepatic arterial treatment or progressive hepatic metastasis after prior regional treatment with trans-arterial embolization. Embolization of hepatic artery with different types of medication will be considered to be one regional treatment.
- 4.13 Willingness and ability to give informed consent.
- 4.14 ECOG performance status of 0, or 1.
- 4.14 Adequate renal and bone marrow functions:
Serum creatinine ≤ 2.0 mg/dl, granulocyte count $\geq 1000/\text{mm}^3$, and platelet count $\geq 100,000/\text{mm}^3$.
- 4.15 Adequate liver function: total bilirubin <1.6 mg/ml and albumin > 3.0 g/dl,

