4.2 Exclusion criteria

- 4.201 Failure to meet any of the criteria set forth in section 4.1.

- 4.202 Significant shunting to the lung (>20%) identified on MAA scan.
- 4.203 Unsuccessful closure of major collateral blood flows from the hepatic artery to non-targeted organs such as the GI tract. Small collaterals that are considered to be safe for Sir-Sphere® treatment by interventional radiologists and radiation oncologists are eligible.
- 4.204 A solitary liver metastasis that is amenable to surgical removal for potential cure.
- 4.205 Presence of symptomatic liver failure including ascites and hepatic encephalopathy.
- 4.206 Presence of life-limiting extra-hepatic metastasis that requires a systemic treatment within 3 months. Patients with extra-hepatic metastasis that can be controlled with a loco-regional treatment are eligible.
- 4.207 Presence of untreated brain metastases. If patients have had previous treatment for brain metastasis, an MRI or CT scan of the brain must confirm the stabilization of the brain metastasis for more than 4 weeks.
- 4.208 Occlusion of the main portal vein, or inadequate collateral flow around an occluded branch of the portal vein as determined by angiography.
- 4.209 Presence of uncontrolled hypertension or congestive heart failure, or acute myocardial infarction within 6 months of entry.
- 4.210 Presence of any other medical complications that imply a survival of less than six months.
- 4.211 Uncontrolled severe bleeding tendency or active GI bleeding.
- 4.212 Significant allergic reaction to iodinated contrast.

- 4.213 Systemic chemotherapy within 2 weeks prior to study entry (signing consent form).
- 4.214 Previous radiation treatment that includes the liver in the main radiation field.
- 4.215 Pregnancy or breast-feeding women.
- 4.216 Biliary obstruction, biliary stent, or prior biliary surgery including sphincterotomy but excluding cholecystectomy.
- 4.217 Previous treatment with isolated hepatic perfusion
- 4.218 Children under the age of 18

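### Criterion 4.15 sets the only bilirubin entry limit in mg/ml (1.6 mg/ml = 160 mg/dl); read literally it does not screen for raised bilirubin, and the unit must be reconciled with the rest of section 4.1

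*Combined protocol and SAP*

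**What the plan says.** Criterion 4.15 in section 4.1 (Inclusion criteria) reads "Adequate liver function: total bilirubin <1.6 mg/ml and albumin > 3.0 g/dl". The criterion just before it (the second one numbered 4.14, introduced by "Adequate renal and bone marrow functions") gives "Serum creatinine ≤ 2.0 mg/dl".

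The limits in section 4.1 are binding. The first exclusion in section 4.2 (4.201) is "Failure to meet any of the criteria set forth in section 4.1".

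Two other exclusions bear directly on the liver or bile ducts: 4.205, "Presence of symptomatic liver failure including ascites and hepatic encephalopathy", and 4.216, "Biliary obstruction, biliary stent, or prior biliary surgery including sphincterotomy but excluding cholecystectomy". Exclusion 4.210 removes patients whose other medical complications imply survival under six months. None of these gives a bilirubin value.

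Bilirubin is named in several other places: footnote 1 of the schedule table, the laboratory tests in sections 5.4, 5.7 and 5.8, and the expected adverse reactions in section 8.4. None of them states a unit or a limit.

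**The concern.** A bilirubin limit in an adequate-liver-function criterion is there to keep out patients whose liver function is already impaired. A limit placed far too high by its unit cannot do that, whatever number was intended.

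The plan itself explains why this matters here. Under radiation hepatitis, section 8.4 identifies "patients with diseases which compromise the functioning of the liver parenchyma" among those who may face a higher risk of liver function impairment. Section 9.1 sets a separate normal-liver dose ceiling for cirrhosis, so patients with impaired parenchyma are foreseen. In the institution's own earlier series (section 1.8), 5 of 12 patients had raised hepatic enzymes at one month.

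Safety is one of the two primary objectives (section 2.11), and grade 3 and 4 laboratory abnormalities are part of the safety endpoint (section 2.2). Section 3.0 ties the second treatment to toxicity grade after the first. With 24 patients planned per group, a few who enter with raised bilirubin could make it harder to separate treatment toxicity from baseline dysfunction.

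**Working it through.** The limit is a stated threshold with no derivation in the plan, so there is no plan figure to reproduce. The check is a unit conversion, followed by a test of what the converted limit would exclude.

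**Inputs, all from section 4.1:** bilirubin below 1.6 mg/ml; creatinine at most 2.0 mg/dl; albumin above 3.0 g/dl.

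**Step 1. Convert the bilirubin limit.** 1 dl = 100 ml, so a value in mg/dl is 100 times the value in mg/ml.

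1.6 mg/ml × 100 ml/dl = 160 mg/dl.

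**Step 2. Compare with the same number in the unit used for creatinine.** 1.6 mg/dl ÷ 100 = 0.016 mg/ml. The ratio of the two readings is 160 ÷ 1.6 = 100. This is a conversion only; it does not establish which limit was meant.

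**Step 3. Put the three limits on one scale.**

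- Creatinine: 2.0 mg/dl ÷ 100 = 0.02 mg/ml.
- Bilirubin as written: 1.6 mg/ml, which is 1.6 ÷ 0.02 = 80 times the creatinine limit by mass.
- Albumin: 3.0 g/dl = 3,000 mg/dl; ÷ 100 = 30 mg/ml.

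Bilirubin is the only one of the three stated per millilitre.

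**Step 4. Test what the written limit excludes.** The documents give no range of bilirubin for candidates, so 2 to 80 mg/dl is an assumption.

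| Assumed bilirubin (mg/dl) | In mg/ml | Below 1.6 mg/ml? | Share of the 160 mg/dl limit |
|---|---|---|---|
| 2 | 0.02 | yes | 1.25% |
| 5 | 0.05 | yes | 3.125% |
| 10 | 0.10 | yes | 6.25% |
| 20 | 0.20 | yes | 12.5% |
| 50 | 0.50 | yes | 31.25% |
| 80 | 0.80 | yes | 50% |

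Every value passes, and the highest reaches only half the limit.

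**Step 5. Look for a correction elsewhere.** No other section states a bilirubin unit or threshold, so nothing overrides or supports the per-millilitre figure. Because 4.201 makes the section 4.1 criteria binding, the written limit is the operative one.

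**The case against.** The strongest reply is that this is an obvious slip. The criterion is about adequate liver function, the neighbouring chemistry limits are per decilitre, and the study runs at one institution whose staff would probably read the figure as mg/dl. That is likely right, and it limits the practical harm. A reader might infer from the arithmetic that the criterion excludes 0% of candidates in practice, or that jaundiced patients will be enrolled. The documents support neither: they contain nothing on how the criterion is applied, and they give no bilirubin values for candidates.

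Other safeguards also remain. In 4.205, ascites and encephalopathy are examples and not a closed list, so an investigator could use it for a jaundiced patient with symptomatic liver failure. The albumin limit ("albumin > 3.0 g/dl"), 4.208 on portal vein occlusion, 4.210, 4.216, the cap on tumor volume at under half the liver, and ECOG 0 or 1 all remove some patients. Section 9.1 limits the dose to normal liver. Meeting 4.15 is therefore not the same as being enrolled. But none of these is a bilirubin threshold, so none does what 4.15 was written to do.

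A reader might also infer that baseline dysfunction will be counted as treatment toxicity. The plan partly deals with this: bilirubin is measured at screening, and section 11.1.2 (Preexisting Conditions) keeps an existing disorder from being reported as an adverse event unless it worsens or recurs more often. What remains is narrower: section 2.2 does not say that its grade 3 and 4 laboratory abnormalities are limited to changes from baseline.

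Finally, the absence of AST, ALT or alkaline phosphatase limits is a design choice and not part of this error.

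**Conclusion.** The point holds for the written text. The only bilirubin entry limit is stated as 1.6 mg/ml, or 160 mg/dl, in a list whose other serum chemistry limits are per decilitre, and it differs by a factor of exactly 100 from the same number in mg/dl. The conversion needs no assumption. The conclusion that the literal limit excludes no one for raised bilirubin rests on the assumed range of 2 to 80 mg/dl and would hold for any set of candidates all below 160 mg/dl.

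How many patients would be wrongly enrolled cannot be estimated from the documents, and the number may be small. The defect still needs correction. If staff silently change the unit, they apply a limit that the protocol does not state. If they follow the text, the limit screens nobody over the assumed range, and a monitor working from the text could not use 4.15 to call a patient with clearly raised bilirubin ineligible. The primary efficacy analysis, sample size and error rates in section 12.0 do not depend on this figure.

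**What to change.** Reconcile the bilirubin unit in 4.15 with the units used in the rest of section 4.1, and have the investigator confirm the limit that was intended. This review proposes no value. Use the confirmed limit and unit wherever eligibility is checked.

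The cost is a one-line protocol correction, reviewed as an amendment under section 14.2, and an update of any eligibility form that repeats the criterion. No new test is needed, because total bilirubin is already in the screening panel. Nothing in section 12.0 has to be recalculated.
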